3.7.7 Data Collection

Data will be collected by the principal investigator, the nurse practitioner, or nutritionist and documented on a standardized data form. The data will be entered by a research coordinator or the principal investigator in a fashion that maintains patient anonymity, using a unique identification number. The data will be entered into a secure computerized database, which can be accessed only by the principal investigator and the research coordinator with the use of a password. Data collection and statistical analysis will be performed by assigned research personnel, who will access the data using the unique patient identification number assigned.

We will collect relevant life history information from the subject's medical records including illnesses and hospitalizations that occur while subjects are participating in the research, as well as age, ethnic background, marital status, medical history, weight loss, changes in weight-related medical conditions, and information about the surgery and information about lap-band adjustments, and complications. We will collect medical information from physicians and other healthcare providers in General Surgery, Pediatric Surgery, Pediatrics, Psychiatry, and Psychology and from the NYU hospital medical records.

All data will be recorded on case report forms and compared at 6, 12, 24, 36, 48, and 60 months with baseline. Results will be reported descriptively as well as by modeling weight loss in order to assess aggregate outcomes and address the issues of safety and efficacy.

3.7.8 Stopping Rules For Adverse Events

The trial will be terminated if two or more patients die due to the surgery. The trial will be terminated if during the follow-up period two or more of the first 25 patients implanted have developed esophageal dilation. The trial will also be terminated if during the follow-up period two or more of the first 35 patients implanted develop a nutritional deficiency.

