1.0 INTRODUCTION

1.1 Background and Rationale

The Lap-Band System is approved by the FDA for use in adults. Studies have demonstrated that childhood obesity increases the likelihood of developing numerous co-morbid conditions, including: hypertension, diabetes mellitus, pulmonary complications, growth acceleration, dyslipidemia, musculoskeletal problems, psychosocial problems, and cancer [1-2]. The severely obese patient faces death without proper treatment of the condition. Furthermore, the economic impact of obesity is substantial. It is estimated that the cost of obesity in the U.S. in 2002 dollars is \$117.1 billion, and, with estimates that obesity could affect two in five adults by the year 2025, the need to address obesity at an early age is clear.

It has been shown that the nutritional and behavior modifications necessitated by bariatric surgery, as evidenced by the reported success of the gastric bypass procedure in adolescents, are safe, and are associated with significant weight loss as well as correction of co-morbid conditions and improved self-image and socialization [3-5]. The use of the Lap-Band System results in clinically significant weight loss with significantly less operative morbidity and mortality than the gastric bypass procedure in adults [6]. Additionally, the adjustability to patient needs and the relative ease of reversal is unique to the Lap-Band System. This system has been used in adults in Europe and other countries since 1993; international publications report a mean Percent Excess Weight Loss (%EWL) of 52% in subjects with 1 year of follow-up and 68% after 2 years of follow-up [7-9]. In the first US clinical study a mean of 34.6% EWL in 221 subjects was reported with 1 year follow-up and 38.2% EWL in 122 subjects at 2 years of follow-up. However, the first published US experience by Rubinstein of 63 patients showed a 53% EWL at 3 years [10]. Currently, our experience in adults demonstrates a 44.3% EWL at 1 year [11]. Finally, the Lap-Band has been shown to be a safe and effective method of weight loss in morbidly obese adolescents by Dolan, et.al., in Brisbane, Australia [12]. In fact, when compared to matched controlled adults, adolescents did better in terms of weight loss and complications [13]. Mortality has been found to be only about 1 in 10,000 [0.01%]; this compares with a mortality rate among gastric bypass patients that approaches 0.5% [6].

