2.0 STUDY OBJECTIVES

2.1 Primary Objective

The primary objective of this research is to demonstrate the safety and efficacy of the use of the LAP-BAND® System in the morbidly obese adolescent population in the United States, and therefore provide these individuals with a significantly less morbid and reversible surgical option for weight loss.

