3.0 INVESTIGATIONAL PLAN

3.1 Study Design

This is a prospective, non-randomized, single-center study to be conducted under an FDA-approved Investigational Device Exemption (IDE). One investigational site will enroll and treat up to 120 subjects who meet the criteria for use of the LAP-BAND® System, except that they are adolescents ages 14 to 17. Subjects will be followed for five years.

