3.7.5 Safety Evaluations

Mortality:

Thirty day mortality will be evaluated to monitor death, which may have been directly related to the intervention.

Esophageal dilation:

The long-term effects of gastric banding on esophageal motility are unknown. The risk of chronic esophageal dilatation with loss of peristalsis is theoretical and unproven. Annual post-operative esophagrams will be performed to monitor esophageal anatomy and band positioning. If necessary, esophageal manometry will be performed to evaluate for esophageal dysmotility if patient presents with dysphagia and abnormal esophagram indicating achalasia.

Nutritional deficiency:

Although there has been no known nutritional deficiency linked with gastric banding, there have been no long-term studies that measure biochemical markers of nutrition or evaluation of eating behavior. Potential nutritional deficiencies will be monitored with annual blood work and nutritional evaluations, as described.

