3.7.10 Data Safety Monitoring Board

The data safety monitoring board will be composed of three independent physicians who expertise in the treatment of obesity, clinical trials, and statistical knowledge.

DSMB will meet quarterly and the location will be determined at least 2 weeks before the meeting date. The main responsibility of DSMB is to monitor data to provide evidence for

safety concerns and recommendations for study continuation, discontinuation, or modification due to benefit vs. harm.

The following data will be reviewed by DSMB.

1. baseline data
2. safety data
3. efficacy data

A third party surgeon, [name], who is not affiliated with NYU SOM and NYU Hospital will serve as the safety monitor.

[name] MD
Co-Director, Children's National Obesity Institute
Associate Professor of Surgery and Pediatrics
The George Washington University School of Medicine & Health Sciences
Children's National Health System
[name]
[name]

The appointed surgeon will monitor the safety data every year and will review all SAEs. All SAEs will be reported to the appointed surgeon within 10 days regardless the relationship to the study procedure.

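### The mortality stopping rule acts only at a second death due to the surgery, with no time window or adjudicator, and no first death is sent to the DSMB between quarterly meetings

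*Combined protocol and SAP*

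**What the plan says.** Section 3.7.8 sets one rule for mortality: "The trial will be terminated if two or more patients die due to the surgery". The two other rules in that section, on esophageal dilation and nutritional deficiency, each refer to the follow-up period and give a denominator (the first 25 and the first 35 patients implanted). The mortality rule has neither. It does not say who decides that a death was due to the surgery, and it attaches no step to a first death.

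The figures that bear on the rule are in Sections 1.1 and 3.1. For the band, Section 1.1 states: "Mortality has been found to be only about 1 in 10,000 [0.01" (per cent). It sets this against a "mortality rate among gastric bypass patients that approaches 0.5" (per cent). Section 3.1 gives the size: "One investigational site will enroll and treat up to 120 subjects". The primary objective in Section 2.1 is to "provide these individuals with a significantly less morbid and reversible surgical option for weight loss".

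A single death is handled elsewhere as a serious adverse event. Section 3.6.3 requires a report to the IRB within one business day, including whether the event was fatal and the investigator's view of its relationship to the test article. Section 3.7.10 adds: "All SAEs will be reported to the appointed surgeon within 10 days regardless the relationship to the study procedure". That surgeon is independent of the institution and reviews every serious adverse event. Under the same section the DSMB meets quarterly, reviews safety data and may recommend that the study stop or change.

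Section 3.7.5 plans a mortality evaluation: "Thirty day mortality will be evaluated to monitor death, which may have been directly related to the intervention". It is not tied to the stopping rule.

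**The concern.** The case for the band rests partly on very low mortality. If that premise is right, a first related death among 120 adolescents would be a surprise, and it is the natural moment for the independent board to look. The rule as written is silent then. It waits for a second death, and whether a death counts depends on an attribution that nobody is assigned to make. The only relatedness judgement the protocol assigns is the investigator's, and it concerns the test article rather than the surgery. A reader also cannot tell whether a death after a late erosion, perforation or explantation, all of which Section 3.6.1 lists as adverse events, would count.

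At stake is whether further adolescents could be implanted after a first related death without the DSMB having considered it. With quarterly meetings, the wait could be about three months.

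**Working it through.** The protocol gives no operating characteristics for this rule, so there is no stated figure to reproduce.

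**Inputs**
- n = 120, the maximum enrolment (Section 3.1).
- p = 0.0001, the band rate (Section 1.1).
- p = 0.005, the bypass rate (Section 1.1). The text says the rate approaches this value, so it is an upper figure.
- p = 0.001, our assumption, used only to show how the cost of a wider trigger could grow.

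**Formulas** (deaths X binomial, independent subjects, every death counted)
- P(X ≥ 1) = 1 − (1 − p)^n
- P(X ≥ 2) = 1 − (1 − p)^n − n·p·(1 − p)^(n−1)

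**At the band rate, 0.01%**
- P(X ≥ 1) = 1 − 0.9999^120 = 0.0119, about 1.2%.
- P(X ≥ 2) = 0.00007.

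**At the bypass rate, 0.5%**
- Expected deaths: 120 × 0.005 = 0.6.
- P(X = 0) = 0.995^120 = 0.5480.
- P(X = 1) = 0.6 × 0.995^119 = 0.3304.
- P(X ≥ 2) = 1 − 0.5480 − 0.3304 = 0.1216. The rule triggers about 12% of the time and is silent about 88% of the time. A Poisson check with mean 0.6 gives 0.1219.
- P(X ≥ 1) = 1 − 0.5480 = 0.4520. A first-death trigger reaches 45% and misses 55%.

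**Sensitivity of the two-death rule**

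| n | true rate | P(at least 2 deaths) |
|---|---|---|
| 100 | 0.5% | 9.0% |
| 120 | 0.4% | 8.4% |
| 120 | 1% | 33.8% |
| 120 | 2% | 69.5% |
| 120 | 3% | 87.8% |

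With 120 subjects, the true rate must be about 1.4% for an even chance of triggering and about 2.5% for an 80% chance. Full enrolment and counting every death as surgical both favour the rule.

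**Chance that a first-death review is called**
- At 0.01%: 1.2%, as above.
- At an assumed 0.1%: 1 − 0.999^120 = 0.113, about 11%.

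The second figure matters because Section 1.1 does not say which deaths its 0.01% counts or over what period. A trigger covering possibly related deaths over five years is wider than a perioperative rate, so 1.2% may be too low.

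**The case against.** The strongest reply is that the two-death rule is an automatic backstop, not the whole system. A reader might infer that it is the only protection against mortality. The documents do not support that: Sections 3.6.3 and 3.7.10 provide IRB reporting within one business day, outside-surgeon review of every serious adverse event, and a DSMB that can recommend stopping. This part of the reply stands. The remaining gap is narrower: nothing brings the DSMB in between quarterly meetings, and nothing makes further implants depend on its review.

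A reader might also infer from the 88% that the rule fails at its own purpose. The protocol never says the rule is meant to detect 0.5%. That benchmark is ours, although Section 1.1 draws the comparison itself. With 0.6 expected deaths, no rule that counts deaths can be sensitive, as the 55% miss for a first-death trigger shows. This stands too.

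A third tempting inference is that the 30-day evaluation in Section 3.7.5 will understate mortality. It does not follow. Section 3.6.1 lists death as an adverse event without a time limit and requires all adverse events to be recorded and summarised. Table I schedules adverse event evaluation at visits through year 5. Later deaths would therefore be captured.

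Finally, the dates limit the benefit. A trial period ending in January 2019 with five years of follow-up implies last implants around January 2014, and the current amendment is dated July 2013. On that inference, a check on new implants would cover about six months of enrolment. The definition of a countable death would still matter throughout follow-up.

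**Conclusion.** The point holds as a low-cost safety improvement, not as an error that invalidates the plan. The rule responds only to a second death, leaves the qualifying death undefined in time and attribution, and is not linked to the DSMB review that already exists. On the protocol's figures, a first death would be an event with about a 1.2% chance, so it deserves prompt independent review.

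Moving to a first-death trigger would raise the chance of a response at a 0.5% rate from 12% to 45%. That is a real gain, but it does not make the trial able to detect a bypass-level rate reliably. These figures assume 120 subjects, independent deaths, and every death counted as related.

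**What to change.** Keep the two-death termination rule in Section 3.7.8 and add three things:

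1. State that the mortality rule covers the five-year follow-up.
2. Name the outside surgeon already appointed in Section 3.7.10 to judge whether a death is possibly related to the procedure, the device or a re-operation.
3. Require that any single death so judged goes at once to an ad hoc DSMB meeting, which decides whether enrolment continues before further subjects are implanted. Section 3.7.10 currently gives the board a power to recommend, so it needs a matching sentence.

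It would also help to state the rule's operating characteristics, so that readers do not expect more of it than 120 subjects allow.

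The cost is protocol wording and an occasional ad hoc meeting; the board and the surgeon are already in place. The downside is a short enrolment delay, with a chance of about 1.2% if 0.01% applies to these deaths, and possibly more: about 11% if possibly related deaths over five years ran at an assumed 0.1%.

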3.7.9 Monitoring the Study

[name] [name]'s designee will monitor the study progress as frequently as is necessary to assure compliance with Good Clinical Practices and protocol procedures and to monitor completion of case report forms. All records pertaining to the study will be made available to clinical research associate at each monitoring visit. The investigational facilities, case report forms, patient records, and all other study documentation will be available for detailed review. Arrangements for monitoring visits will be agreed in advance of planned visits, except in the case of an emergency. FDA representatives reserve the right to visit sites at any time.

3.7.10 Data Safety Monitoring Board

The data safety monitoring board will be composed of three independent physicians who expertise in the treatment of obesity, clinical trials, and statistical knowledge.

DSMB will meet quarterly and the location will be determined at least 2 weeks before the meeting date. The main responsibility of DSMB is to monitor data to provide evidence for

safety concerns and recommendations for study continuation, discontinuation, or modification due to benefit vs. harm.

The following data will be reviewed by DSMB.

1. baseline data
2. safety data
3. efficacy data

A third party surgeon, [name], who is not affiliated with NYU SOM and NYU Hospital will serve as the safety monitor.

[name] MD
Co-Director, Children's National Obesity Institute
Associate Professor of Surgery and Pediatrics
The George Washington University School of Medicine & Health Sciences
Children's National Health System
[name]
[name]

The appointed surgeon will monitor the safety data every year and will review all SAEs. All SAEs will be reported to the appointed surgeon within 10 days regardless the relationship to the study procedure.

4.0 Ethics

4.1 Ethical Principles

This study will be conducted in accordance with Title 21 of the Code of Federal Regulations, Part 812 on Investigational Device Exemptions. Specifically, this study is based on Good Clinical Practices; the study will be conducted under a protocol reviewed by the New York School of Medicine Institutional Board of Review Associates (IBRA); the study is to be conducted by scientifically and medically qualified persons; the benefits of the study are in proportion to the risks; the rights and welfare of the subjects will be respected; the physicians conducting the study will ensure that the hazards do not outweigh the potential benefits; the results to be reported will be accurate; subjects will give their informed consent and will be competent to do so and not under duress; and the ethical principles in Title 21 of the Code of Federal Regulations will be complied with.

4.2 Informed Consent

This study will be conducted in full compliance with the informed consent regulations in 21 Code of Federal Regulations 50. Written informed consent will be given by all subjects participating in this study in accordance with the 21 CFR 312, 600, and 812. The consent form must be reviewed and approved by the IBRA prior to initiation of the study. The consent form must contain a full explanation of the possible advantages, risks, alternate treatment options, and availability of treatment in the case of injury, in accordance with Title 21 of the Code of Federal Regulations. The consent should also indicate that, by signature, the subject, or where appropriate, legal guardian, permits access to relevant medical records by representatives of the FDA.

The investigator is responsible for obtaining written consent from potential subjects prior to performing any trial tests or assessments required by the protocol. A copy of the signed consent document will be given to the subject and the original retained by the investigator with the site's copy of the case report forms.

4.3 Institutional Board of Review Associates (IBRA)

This study will be conducted in full compliance with the New York University School of Medicine Institutional Board of Review Associates policies and procedures and the regulations in 21 CFR 812 and 56.

This protocol will not be initiated unless it has been reviewed and approved by, and remains open to continuing review by the IBRA meeting the requirements of 21 CFR 812.42. The IBRA shall review and have the authority to approve, require modification of (to secure approval), or disapprove the protocol. The IRB shall notify the investigator in writing of its decision. The IBRA shall require that the information given to subjects as part of the informed consent is in accordance with 21 CFR 812.43 and 50.25. The IBRA shall conduct continuing reviews of the protocol at intervals appropriate to the degree of risk, but not less than once per year. Further, at the completion or early termination of the trial, a final report should be made to the IBRA by the investigator within 90 days.

Any change or revision in the protocol that significantly affects the safety of the subjects, the scope of the investigation, or the scientific quality of the trial must be approved by the IBRA prior to implementation. However, any protocol change intended to eliminate an apparent immediate hazard to the subject may be implemented immediately if the FDA is subsequently notified of the amendment by the investigator and the IBRA is informed by the investigator. [21 CFR 812.40]

It is the investigator's obligation to maintain an IBRA correspondence file, and to make this file available for review as part of the trial monitoring process. [21 CFR 812.140]

6.0 Table I

Schedule of Visits and Procedures

Procedure	Screening	PreOP	OP	Visit 1	Visit 2	Visit 3	Visit 4	Visit 5	Visit 6	Visit 7,9,11,13	Visit 8,10,11,14	>18 yrs old (high school graduation)
				Week 1-2	Week 6	3 m	6 m	9 m	1 Y	Every 6m	2 Y, 3Y, 4Y, 5Y	
Informed Consent	X								X		X	
Additional IC for high school grades												X
Inclusion/Exclusion Criteria	X											
Complete Physical Exam	X								X		X	
Demographics Information	X											
Medical History	X											
Wt Loss History	X											
Co-morbidities and Concomitant Medications	X								X	X	X	
Lap-Band Implant/Revision			X									
Lap-Band Adjustment*				X	X	X	X	X	X	X	X	
Follow up Clinical Assessment				X	X	X	X	X	X	X	X	
Labs												
Metabolic Panel		X				X	X	X	X		X	
Hematology Panel		X				X	X	X	X		X	
Thyroid Panel		X				X	X	X	X		X	
Lipid Panel		X				X	X	X	X		X	
Hepatic Function Panel		X				X	X	X	X		X	
Nutritional Panel		X				X	X	X	X		X	
HbA1c & Insulin		X				X	X	X	X		X	
OGTT*		X							*X		*X	
Urinalysis		X							X		X	
Serum Pregnancy Test (If female)		X							X		X	
EKG		X							X		X	
Pulmonary Function Test (If indicated)		X							X		X	
Chest X-Ray		X										
Gall bladder ultrasound		X										
Bone Density		X										
Gastrointestinal Evaluation												
Esophagram		X							X		X	
Esophageal manometry (if necessary)		X							X		X	
Sleep Apnea Test (if indicated)		X							X		X	
Psychiatric Evaluation												
Psychiatric Assessment*	X					*X	*X		X		X	
Child Depression Inventory	X								X		X	
Three-Factor Eating Questionnaire	X								X		X	

Child Behavior Checklist	X								X		X	
Youth Evaluation Scale	X								X		X	
SF-36 Health Survey	X								X		X	
Nutritional Evaluation												
Initial Nutritional Assessment	X											
Follow up Nutritional Assessment		X	X	X	X	X	X	X	X	X	X	
Adverse Event Evaluation		X	X	X	X	X	X	X	X	X	X	

*OGTT will be performed at 1 year and 5 year on the subjects who have impaired glucose tolerance at baseline testing (excluding subjects who have type I or II diabetes wh is not clinically safe to perform the test). However, if the HbA1c or fasting blood glucose test show abnormal results or the subject develops polyuria or polydipisa, additional testing should be performed based on ADA guidelines.

*Additional follow up psychiatric assessment will be performed at 3 months and 6 months for the patients with antidepressants and moderate to severe psychiatric history.

Attachment for data sharing

Adolescent Lap-Band IDE (ALIDE) Study Group

Mission and Scope

Introduction

Obesity has become the most common life threatening disease affecting children in the United States. Bariatric surgery has been suggested as the only reliable means effecting significant weight loss in morbidly obese children, and protocol-controlled research into the application of the LapBand in treatment programs for adolescent obesity has been ongoing since 2005. The FDA will soon consider approving the use of the LapBand in treatment programs for adolescent obesity. Thus, results of the previous and ongoing research will be vital to the FDA considerations and to the obese adolescents who need access to surgery. These results need to be pooled, presented at the FDA panel, and published so as to best advocate for FDA extension of the indication for the device to ages less than 18, and to advocate for morbidly obese adolescents who currently have only the gastric bypass as a surgical option.

Independent IDE Studies

In 2001 the FDA approved the LapBand for use in morbidly obese adults. They specifically listed age less than 18 years as a contraindication to the use of the LapBand. In 2004, [name] of the University of Illinois at Chicago went to the FDA meeting regarding the LapBand and adolescents. Once again, use of the LapBand in children less than 18 years old was not approved. After that [name] worked with [name], [name] and [name] to get an Investigational Device Exemption (IDE) from the FDA to study the LapBand in morbidly obese adolescents in a weight management program at the University of Illinois at Chicago – IDE #1. Subsequent to that, the group at the University of Illinois at Chicago worked with groups at New York University (Drs [name], [name], [name]), at Morgan Stanley Children’s Hospital ([name]), and at A.I. Dupont Children’s Hospital ([name]) as they obtained IDE’s number 2,3, and 4 respectively. The only support from Allergan for these studies was the donation of LapBands to the University of Illinois at Chicago. Each group developed unique methods to fund their studies. These 4 groups now have a

combined experience with over 150 morbidly obese adolescents who have used the LapBand in a multidisciplinary weight management program. These patients are 1-5 years out from the placement of their LapBand and have been managed with very similar protocols. All their studies are IRB approved at their local institutions and the pooled results will be acceptable for journal publication.

ALIDE Study Group

Recognition of the problem of morbidly obese children has increased greatly over the last ten years. Many organizations and many grants and studies have occurred to work on prevention of obesity in children. However, 20-50 % of different populations of children have BMI's that are already over the 95th %tile for their age and gender. These children are already obese and prevention is not appropriate for them. Very little work and study has been done on effective therapy for morbidly obese children. The TeenLabs study from the NIH has published data on comorbidities of morbidly obese adolescents, resolution of comorbidities with successful weight loss with gastric bypass surgery in morbidly obese adolescents, and the short term morbidity and mortality of gastric bypass surgery in morbidly obese adolescents.

The groups at the University of Illinois at Chicago and New York University have individually published short term safety and efficacy, as well as resolution of comorbidities, in morbidly obese adolescents after LapBand surgery. The opportunity now exists for the groups with IDE's #1,2,3, and 4 to pool their data on the safety and efficacy of the LapBand in morbidly obese adolescents. This data would be useful for the upcoming FDA panel consideration of the LapBand in morbidly obese adolescents as it will have as many, if not more, patients as the industry-sponsored multicenter trial and many patients will have longer follow-up. Furthermore, these data should be published as the most extensive data so far from weight management programs for morbidly obese adolescents that utilize a surgical approach.

Project Plan and Output:

The adolescent LapBand IDE Study Group (ALIDE) was formed to achieve pooling of the data from the IDE's at the University of Illinois at Chicago, New York University, Morgan Stanley Childrens Hospital, and A.I. Dupont Children's Hospital. Also included in ALIDE study group are [name] and [name], who were part of the initial IDE work but have since left the institutions listed above.

The ALIDE study group will contact and coordinate with each of the investigators and institutes to acquire a copy of their study data which will be provided to the ALIDE Study group in a de-identified manner, such that no patient can be identified by the ALIDE Study group. The ALIDE Study group will then pool the data from each institute, further de-identifying the patients prior to evaluating and analyzing the data by linear modeling. The data will then be prepared for publication, in a peer-reviewed journal. The data will also be presented to the FDA Pediatric Advisory Committee in the fall of 2010 to support the use of the LabBand in adolescents.

Plan of Action

1. IRB Approval

The ALIDE Study Group project coordinator, [name], will work with each site to achieve IRB approval for the ALIDE Study group project which is to acquire a copy of the de-identified patient data from the four institutions, followed by pooling and analysis of the data and then publication.

Key Personnel at each Site:

NYU: [name]

UIC: [name] and [name]

A.I. Dupont: [name]

Morgan Stanley:

2. Data Transfer

The data will be transferred electronically in a secure manner from each study site as laid out in the ALIDE Study Group Data Transfer Protocol dated March 31, 2010 (Appendix 1). This SOP ensures that patient data is deidentified by the participating site such that any information that can be used to independently identify the identity of any patient will be removed or replaced with non-specific information prior to the data transfer to ConscienHealth. The data will then be deidentified again prior to the pooled data analysis. Note, the data will not be transferred from the ALIDE Study Group secure site once received.

3. Data Analysis

The data from each institute will be pooled and further de-identified prior to evaluating and analyzing the data by linear modeling. The ALIDE study group has identified and agreed upon the data fields (Appendix 2) for which they hope to acquire data from each institute to complete the pooled analysis. The agreed upon data fields will not include date of birth, if needed age will be calculated or estimated.

4. Publication/Presentation

Once the data analysis is complete the data will then be prepared for publication in a peer reviewed journal deemed appropriate by the ALIDE study group and the investigators from each site. The data will also be presented to the FDA Pediatric Advisory Committee in the fall of 2010 to support the use of the LabBand in adolescents. In all publications/presentations the lead investigator from each site and the institution will be acknowledged for their involvement in the project.

APPENDIX 1

ALIDE Study Group Data Transfer Protocol

Approved: March 31, 2010

Prior to transfer

- Each participating site will be provided with the specific data element requirements that will need to be included with the submission package.
- All data will be submitted in an electronic format.
- Prior to submission, the data will be de-identified by the participating site such that any information that can be used to independently identify the identity of any patient will be removed or replaced with non-specific information.
- Each patient will be assigned an identification number and the information linking an identification number with the patient will be held by the participating site and not distributed to any groups outside the participating site.
- Following the collection and preparation of the data in a suitable electronic format, the data will be transferred, as follows.

Data Transfer

- Each site will be provided with a URL (address) for a secure web server.
- Security will be established using SSL and identification accomplished by using self-signed certificates. Each site will be provided with a guide to ensure that the certificates are accepted by the browser and a connection with the web server is established. Due to the limited number of participating sites, a certificate signed by an outside agency will be not obtained.
- Prior to allowing data transfer, the web server will ensure that a secure connection is established; if the connection is established using an insecure mechanism, the client will be redirected automatically to the secure mechanism.
- The participating site will be presented with an authentication page to provide both a user ID and a password; both will be provided with the data requirements package.
- Upon successful authentication using user ID, the site will be presented with a page to select a file to download. The participating site will then download a file with the de-identified data to the secure web server.

Following Transfer

- Following transfer, the web server will move the copied file to a secure, web non-accessible location. Following transfer, the data file will no longer be available to the participating site, or any other public site.
- The information package will no longer be distributed through the public internet but will be physically transferred using portable electronic methods or using private and secure networks.

Data Safeguards

- File transfer will be only allowed using SSL encrypted file transfer protocols.
- Authentication and data upload will be only allowed for participating sites and will be secured by unique passwords and user information.

- In the unlikely event that the transferred data is intercepted or otherwise is obtained, the information will not contain information that will allow for the independent identification of individual patients, but will require further information held by the participating site to allow patient information.
- The information to allow identification of patients will not be requested by the study and will not be transferred outside of the study site.

APPENDIX 2

Data Field Request- June 2010

1	Age at surgery (Date of birth will not be given, if needed age will be calculated or estimated)	
2	Height at surgery	
3	Weight at surgery – before preop diet	
4	BMI at surgery - before preop diet	
5	Duration of surgery (if data exists)	
6	Age at onset of obesity (if data exists)	
7	Length of preop preparation – months (not needed for FDA)	
8	Length of hospitalization - days	
9	Operative complications – list	
10	Readmissions within 30 day post op – Y/N	
11	Preop comorbidities a) OSA b) Pseudotumor cerebri c) Hypertension d) Abnormal EKG e) Abnormal cardiac ECHO f) Asthma g) GERD h) NASH	i) PCOS j) SCFE k) Diabetes l) Prediabetes – abnormal GTT or elevated fasting insulin m) Hyperlipidemia n) Kidney disease
12	Preop Evaluations a) EKG (if data exists) b) Cardiac ECHO (if data exists) c) Fasting glucose d) Fasting insulin e) GTT f) LFT's	g) Lipids h) Nutritional Panels (if data exists) i) Quality of life evaluations (if data exists) j) Depression questionnaire (if data exists)
13	Items monitored post op – 3 months, 6 months, 9 months, 12 months, 18 months, 2 years, 2.5 years, 3 years, 3.5 years, 4 years, 4.5 years, 5 years a) Height b) Weight c) BMI d) EKG (if data exists) e) Cardiac ECHO f) Fasting glucose (yearly only) g) Fasting insulin (yearly only)	k) Nutritional Panels (if data exists) l) Quality of life evaluations (if data exists) m) Depression questionnaire (if data exists) n) GTT (yearly only) o) LFT's (yearly only) p) Lipids (yearly only) q) Nutritional Panels (if data exists) r) Quality of life evaluations (if data exists)

	
 h) GTT (yearly only) i) LFT's (yearly only) j) Lipids (yearly only) 	
 s) Depression questionnaire (if data exists)
14	Healthcare issues post op 
 a) Hospitalizations b) Operations c) New medical problems 	
15	Post op care (if data exists) 
 a) Scheduled visits to weight management program – each year b) Unscheduled visits to weight management program – each year c) AGB adjustments – each year
